- 2) Small diameter retraction cord, after it has been hydrated with Hemodent for 10 minutes, is tucked around the tooth in the space between it and its surrounding gum tissue. A second larger diameter retraction cord, also hydrated with Hemodent, will be placed over the first cord and tucked around the tooth. These cords will be left in place for a minimum of 8 minutes. These cords temporarily push the gum tissue back away from the tooth. (Before making the impression, the 2nd larger cord is removed, and the gums will stay back long enough for the impression material to seep around the tooth, thus allowing it to capture a copy of the entire tooth preparation.)
- 3) After a minimum of 8 minutes, the larger 2nd cord will be removed, and the tooth dried. Quickly, after confirmation of a dry field, the light body consistence impression material is syringed around the prepared tooth and across the occlusal surfaces of adjacent teeth.
- 4) An impression tray that has been filled with the heavy body consistency impression material is then placed over the arch of teeth, and gently pressed into place to ensure the teeth are completely covered with a uniform thickness of impression material. As the different impression material consistencies set, they fuse together into a single unit.
- 5) When removed from the mouth, the impression should contain a negative copy of both the prepared tooth and the teeth of that jaw.

Cordless Impression Procedure:

- 1) The prepared tooth is washed and dried, and assure hemostasis.
- 2) Apply B4 + surface optimizer.
- 3a) If 1 prepared tooth requiring an indirect restoration is being impressed, a single size (0.7mL) unit dose cartridge will be inserted into the digit power dispenser. If more than 1 prepared tooth requiring an indirect restoration is being impressed, a multi size (1.6mL) unit dose cartridge will be inserted into the digit power dispenser.
- 3b) Using the digit power dispenser, unit dose cartridge, and intrasulcular mixing tip, depress foot pedal and gently insert tip into the gingival sulcus of the prepared tooth, slightly apical to the preparation finish line. Material should flood the sulcus. Make sure to dispense material ahead of the intrasulcular tip, and completely around the prepared finish line, and then the tooth.

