- 4) An impression tray that has been filled with the heavy body consistency impression material is then placed over the arch of teeth, and gently pressed into place to ensure the teeth are completely covered with a uniform thickness of impression material. As the different impression material consistencies set, they fuse together into a single unit.
- 5) When removed from the mouth, the impression should contain a negative copy of both the prepared tooth and the teeth of that jaw.

The clinician will record the impression technique, type of impression material used; whether tray adhesive was used; the tray material; the type of tray used; the number of units requested; the time required to obtain the first impression (start and end of impression taking is defined above for each procedure), and the total number of impressions produced until an adequate impression was made. Also recorded will be the clinic and resident year if placed in a graduate clinic and the subject's age and sex. Unique id numbers not related to clinical record will be used.

The impressions will be photographed, digitally scanned, saved in black and white, and then collectively evaluated at a later time based on a criteria evaluation form by two calibrated evaluators. The evaluators (also referred to as expert examiner) will assess each impression for errors in the finish line; in the tray/material; and errors with gingival displacement/hemostasis as primary outcomes. The number of errors can range from 0 to 13.

Patient discomfort will be assessed using the FACES visual picture pain scale rated from 1-10 based on the following question posed at 4 points during treatment; "How much discomfort are you experiencing at this point in treatment?" This question will be asked at the beginning of the treatment appointment, immediately before the impression procedure is initiated, immediately after the impression procedure is completed, and again at the completion of the treatment appointment. Each question will be rated on a scale of 1 to 10. The total score indicated by the sum of the 4 questions will be analyzed.

Patient consent will be obtained prior to treatment and the impression. This may occur at a prior treatment planning visit or at the treatment visit.

Inclusion Criteria:

- Patients must be adult males or females 18 years of age or older.
- Patients must be able and willing to follow study procedures and instructions.

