- Patients must have read, understood and signed an informed consent form.
- Patients must be in good general health, (based on a review of the medical history, blood pressure and heart rate).
- Patients must have no health-related contra-indications to dental treatment.
- Patient must require at least one indirect restorations (crowns).
- Probing pocket depths around the treatment tooth/teeth must be 4mm or less.
- There must be no bleeding on probing around the treatment tooth/teeth.
- The prepared finish line must be between 0 to 1mm sub-gingival (inclusive).

Exclusion Criteria:

- Individuals who have a chronic disease with oral manifestations.
- Individuals who exhibit gross oral pathology.
- Smokers
- Uncontrolled Diabetics (per review of medical history)
- Probing pocket depths around treatment tooth/teeth of greater than 4mm.
- Bleeding on probing around treatment tooth.teeth.
- The prepared finsh line is greater than 1mm sub-gingival.

The inclusion/exclusion criteria limit generalizability of the findings to patients without confounding periodontal or medical issues. However, the sample size of this study is not sufficient to extend to a consideration of the effect of these confounders on the comparison of the two impression techniques.

The proposed research study requires a total of 100 participants. Patients will be recruited from and will be treated in the Dental Faculty Practice, the Graduate Operative Clinic, and the Graduate Prosthodontic Clinic. The patient may seek other dental treatments in the above mentioned clinics or in other clinics in the School of Dentistry.

Study clinicians will be trained and calibrated on both the cordless and the corded gingival displacement procedures and impression procedures in a practice session. Clinical instruction protocols will be printed on laminated forms for all study clinicians to follow, for both the cordless and the corded procedures. These clinical protocol forms will be in the clinicians operatory during actual study treatment, and this protocol must be followed for the impression to be included in the study. The clinical instruction protocol is listed in Appendix A.

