All of the impressions will be photographed and digitally scanned, and saved in black and white. These scans will be evaluated collectively on a later day, and will be critiqued based on a criteria form (See Appendix B). This evaluation will be performed by 2 calibrated expert examiners for all impressions, and will be completed independently. If a conflict exists in evaluations between examiners, the examiners will meet to form a consensus response. Impressions will be deemed acceptable or not acceptable, and the reasons for not acceptable impressions will be indicated. The evaluation criteria are listed in Appendix B.

In an effort to reduce bias in reviewing the impressions, all of the images will be black and white so not to clue the examiners into which color of impression material was used, which could be correlated with each technique.

The scientific knowledge to be gained will be the efficacy of a new gingival displacement procedure, and if it can be adopted to improve patient treatment and treatment outcomes.

The risks of the study are consistent with the current standard of care. Standard treatment protocols will be observed for the treatment of teeth which require indirect restorations. The risks will be minimized by

treatment evaluation and proper treatment technique.

Data monitoring

Research data management will involve collection, entry, processing, storage, retrieval, archival, distribution and documentation of information. Data collection will adhere to precise written forms. Data will be stored in a series of Microsoft Access data files, which will be accessible to the Investigators and their staff. Only project-related personnel will be able to access these files. Data collection forms will be kept in locked files. Quality assurance (QA) will occur as data is entered in order to check for data completeness and consistency prior to entry.

Statistical Analysis:

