Descriptive statistics for all study variables will be computed by impression group and used to summarize the procedural materials used in the impression and the outcomes. The primary outcomes are the number errors of the impression in the finish line; in the tray/material; and errors with gingival displacement/hemostasis (number of errors can range from 0 to 13), the time to complete the impression, and patient discomfort (range from 0 to 40). Since the outcomes are unlikely to be normally distributed, the Wilcoxon rank sum test will be used as the primary statistical test to assess whether the quality of impressions, time, or patient discomfort made with a cordless gingival displacement procedure is different than with a corded technique. To adjust for additional covariates [clinic providing care, jaw, procedural materials], Poisson regression will be used to assess the relationship between the primary outcomes and the covariates of interest, including impression group with a primary interest in estimation using confidence intervals.

The lack of historical data comparing the proposed outcomes between the two impression groups makes a sample size calculation difficult. For this exploratory study which is time constrained as a thesis project, a sample size calculation was done using an effect size which may be larger than the clinically meaningful effect size. A sample size of 30 in each group will have 80% power to detect a probability of 0.709 that an observation (number of total errors) in the Cordless group is less than an observation in the Corded group using a Wilcoxon (Mann-Whitney) rank-sum test with a 0.05 two-sided significance level.

Budget

Materials	Amount needed	Estimated costs
Aquasil Ultra Cordless Pneumatic Power Dispenser Units (3)	3 systems	Included in normal clinic treatment
Aquasil Ultra Cordless PVS material	Enough for 30 impressions + 10 for practice calibration.	Included in normal clinic treatment
Aquasil Ultra Cordless B4 Pre-Impression Surface Optimizer	Enough for 30 impressions + 10 for practice calibration.	Included in normal clinic treatment
Aquasil Ultra Cordless Ultrathin intra sulcular tips	Enough for 30 impressions + 10 for practice calibration.	Included in normal clinic treatment
Aquasil Ultra PVS materials (heavy and light body)	Enough for 60 impressions + 10 for practice calibration.	Included in normal clinic treatment

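### The adjusted Poisson model includes an unlisted set of procedural materials; if type of impression material is among them, it duplicates the arm and the adjusted technique effect cannot be estimated, or only very imprecisely

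*Combined protocol and SAP*

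**What the plan says.** The Statistical Analysis section names an unadjusted comparison as primary: "the Wilcoxon rank sum test will be used as the primary statistical test". It then adds a model: "To adjust for additional covariates [clinic providing care, jaw, procedural materials], Poisson regression will be used to assess the relationship between the primary outcomes and" further terms. Impression group is a term in that same model, "including impression group with a primary interest in estimation using confidence intervals". The section does not say which items count as procedural materials. Its opening sentence uses the same expression for what goes into making the impression.

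The Methods section lists the items recorded: "The clinician will record the impression technique, type of impression material used; whether tray adhesive was used; the tray material; the type of tray used". For impression material, the form completed by the treating clinician gives two options, Aquasil Ultra Cordless and Aquasil Ultra. It gives five tray materials, three tray types and yes or no for adhesive.

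The two procedures in Methods differ in more than the use of cord. The cordless procedure has its own preparatory step ("Apply B4 + surface optimizer"), a unit dose cartridge, a powered dispenser and an intrasulcular tip. The corded procedure uses two cords, Hemodent and syringed light body material. The tray-filling step with heavy body material is the same in both. On adherence, Methods says that "this protocol must be followed for the impression to be included in the study". On masking of the evaluators, it refers to "which color of impression material was used, which could be correlated with each technique".

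**The concern.** A covariate that is set by the arm cannot be held constant while the arm is varied. If type of impression material stands beside impression group, the model is asked to separate two columns that carry the same information, or nearly so.

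The adjusted model is the only place where the plan specifies confidence intervals for the technique effect, and it is to be fitted to all three primary outcomes (errors, time and discomfort). In a study that calls itself exploratory, those intervals are likely to be what readers use to judge the size of any difference.

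Tray material, tray type and adhesive raise a weaker question. The envelope is opened after tooth preparation, and the documents do not say whether the tray and adhesive are chosen before or after that. If they are chosen afterwards, they could respond to the allocation, and adjusting for them could absorb part of the effect of the technique.

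**Working it through.** **The plan's own figure.** Inputs from Statistical Analysis: probability 0.709, 80% power, two-sided 0.05. Noether's formula for two equal groups gives N = (1.960 + 0.842)² / [12 × 0.25 × (0.709 − 0.5)²] = 7.849 / 0.1310 = 59.9 in total, so 30 per group. The stated size reproduces. It is for the unadjusted Wilcoxon test, so nothing below changes it.

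**Is material tied to arm?** Three places point that way. The procedures give each arm its own sulcus material and delivery. The Budget provides Aquasil Ultra Cordless material for 30 impressions plus practice, which is one planned group of 30. The adherence rule leaves little room for impressions made with the other arm's material.

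**Exact overlap.** Count the columns: intercept 1, arm 1, clinic 2, jaw 1, adhesive 1, tray material 4, tray type 2, total 12. With simulated covariates this matrix has rank 12, so the arm effect can be estimated. Adding material coded identically to arm gives 13 columns, still of rank 12. The result is the same at 60 and at 100 patients.

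A Poisson simulation shows the effect on output (assumed: mean of 2 errors, rate ratio 0.6, true log ratio −0.511, 60 patients). Without material, the average arm coefficient was −0.514. With material added, a minimum-norm fit gave −0.257 to arm and −0.257 to material, an arbitrary half each. Software that drops the material column instead returns the same arm estimate as the model without it.

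**Near overlap.** Suppose m patients in each arm of n have the other arm's material (an assumption; the documents give no rate). The arm–material correlation is r = 1 − 2m/n, and the variance inflation for arm is 1/(1 − r²). For m = 1 and n = 50: r = 0.96, and 1/(1 − 0.9216) = 12.8. The square root is 3.6.

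| Per arm (n) | Mismatches per arm (m) | r | Variance inflation | SE multiplier |
|---|---|---|---|---|
| 50 | 1 | 0.96 | 12.8 | 3.6 |
| 50 | 2 | 0.92 | 6.5 | 2.6 |
| 50 | 5 | 0.80 | 2.8 | 1.7 |
| 30 | 1 | 0.93 | 7.8 | 2.8 |
| 30 | 2 | 0.87 | 4.0 | 2.0 |
| 30 | 5 | 0.67 | 1.8 | 1.3 |

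Both sizes are shown because recruitment is set at 100 (taken as 50 per arm) while the power statement uses 30 per group. The formula considers material as the only other covariate and weights patients equally, so for a Poisson model it is approximate.

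For scale: in the simulation with 100 patients and no material term, the average standard error of the log ratio was 0.173. An interval centred on 0.6 then runs from 0.6/e^(1.96 × 0.173) = 0.43 to 0.84. Multiplying the standard error by 3.57 gives 0.618, and the interval becomes 0.18 to 2.0.

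**Tray variables alone.** Simulated as independent of arm, the full set of adjustment covariates without impression material (clinic, jaw, adhesive, tray material, tray type) gave a variance inflation for arm of about 1.1 to 1.2. These variables do not break the model. The only question about them is when they are chosen.

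**The case against.** The strongest reply is that the premise is inferred. The plan never says that impression material is one of the adjusted procedural materials. Four items are recorded, three of them are not assigned by arm, and a model with only those three has full rank. That stands, so the point is conditional. It does not remove the point: nothing excludes impression material, it is the first material recorded, and an analyst following the text could reasonably enter it.

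A second reply is that one-to-one mapping is not stated. The masking paragraph says only that colour could go with technique. Methods describes the cordless arm as using Aquasil Ultra polyvinyl siloxane, and the Budget covers Aquasil Ultra heavy and light body for 60 impressions. A cordless patient's form might therefore show both materials. This too is fair, but an indicator for the Cordless product would still follow the arm.

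Third, the primary Wilcoxon test has no covariates, and exact overlap would show itself when the model is fitted. Both are correct. They limit the damage to the adjusted model, and they make near overlap the more troublesome case, because the model then fits without complaint.

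A reader might infer three stronger things that the documents do not support:

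- *That adjustment removes the technique effect.* Under exact overlap the coefficient is unidentifiable; the effect is not shown to be zero.
- *That the aims cannot be answered because the arms differ in material and delivery.* The arms are defined by named products in current use, and in the cordless procedure the dispensed material itself floods the sulcus. Comparing two whole procedures is a legitimate question, and the randomised contrast answers it.
- *That tray choices follow allocation.* The procedures show the tray being placed after displacement, but do not say when it is chosen.

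**Conclusion.** The point holds in conditional form and is moderate, not a must-fix. The covariate list is open, and its natural reading brings in a variable that the procedures tie to the arm. If that variable is entered, the adjusted technique effect is unidentifiable under exact overlap. Under near overlap it is very imprecise: the standard error is about 3.6 times larger with one mismatch per arm of 50, and 2.8 times with one per arm of 30. These multipliers rest on assumed mismatch counts.

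The primary test, its sample size and the comparison of the two procedures as wholes are sound on this point. One matter of interpretation follows: a difference between arms belongs to the complete procedure, including wash material, delivery and surface optimizer. It cannot be credited to displacement alone. Some errors scored in Appendix B, such as lack of polymerization or tearing, may reflect the material.

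**What to change.** In Statistical Analysis, replace the procedural-materials term with a named list. Adjust for clinic and jaw, both settled before the envelope is opened. State that type of impression material, and anything else determined by the arm, is not a covariate. Report tray material, tray type and adhesive descriptively by arm, or adjust for them only if the choice is written on the clinician form before the envelope is opened. When results are reported, say that the contrast is between two complete procedures. The aims need no rewording for this.

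The cost is a sentence in the analysis section and, if tray adjustment is wanted, a recording step on the form. The downside is small: any precision that tray variables would have added is given up unless they are recorded in time. Sample size and primary test stay as they are.

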More effective and efficient gingival displacement procedure can lead to clinically improved fixed restorations, less patient chair time, and less patient discomfort.

Materials and Methods: One hundred (100) patients will be recruited from the University of North Carolina (UNC) School of Dentistry (SOD). A stratified block randomization will be used to randomize patient to impression technique: Aquasil Ultra Cordless, Dentsply International using Aquasil Ultra Polyvinyl siloxane (PVS) impression material versus Dentsply International, gingival displacement cord (Ultrapak, Ultradent Products International) hydrated with aluminum chloride hexahydrate (Hemodent, Premier Dental Products Company). Stratification will be based on the clinic where treatment is provided (Dental Faculty Practice, Graduate Operative Dentistry, Graduate Prosthodontic Clinic), A block size of 4 within each stratum will be used to maintain a balanced allocation to impression group. Patient inclusion criteria include: 1) requires indirect restoration 2) probing depths 4mm or less. 3) No bleeding on probing. 4) finish line 0-1mm sub-gingival.

Specific Aims

The intent of this exploratory study is to compare two methods (cordless vs corded gingival displacement) currently used in clinical practice to displace sulcular tissues to facilitate an acceptable dental impression that accurately captures the prepared cervical finish line for the fabrication of indirect fixed prosthodontic restorations. The primary aims are to compare the two methods with respect to 1) the accuracy of the impression with respect to capturing the prepared cervical finish line for the fabrication of the indirect fixed prosthodontic restoration as assessed by two expert clinicians 2) the time required to prepare the impression and 3) the discomfort of the procedure as reported by the patient. Secondary aims are to estimate the effect of clinician experience (resident level vs faculty) and jaw of restoration placement (maxillary vs mandibular) on the outcomes of accuracy, time, and discomfort.

Significance

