GingiBraid retraction cord	12 containers- sizes: 00,0,1,2; (3) of each.	Included in normal clinic treatment
Hemodent	3 bottles + 1 for practice calibration	Included in normal clinic treatment
Viscostat	60 disposable vial/syringe	Included in normal clinic treatment
Impression trays	60 trays + 20 for practice calibration	Included in normal clinic treatment
Impression tray adhesive	3 bottles + 1 for practice calibration	Included in normal clinic treatment
Estimate Total:		

Timeline

The study is planned to last approximately 1.5 years to allow for recruitment and data collection and analysis. The study would ask the participants to come to 2 appointments; it might be possible to consent the patient and perform treatment on the same day, if the patient was scheduled for treatment that day already.

TO BE COMPLETED BY TREATING CLINICIAN:

Patient did not meet inclusion/exclusion criteria and is dropped from the study

Medical/smoking

Probing pocket depths around treatment tooth/teeth of greater than 4mm.

Bleeding on probing around treatment tooth/teeth.

The prepared finish line is greater than 1mm sub-gingival

Patient meets inclusion/exclusion criteria

Patient ID: _____

Impression Group: _____ *Corded* _____ *Cordless*

Clinic: _____ *Dental Faculty Practice*

_____ *Graduate Operative Clinic* _____ *1st* _____ *2nd* _____ *3rd*

_____ *Graduate Prosthodontic Clinic* _____ *1st* _____ *2nd* _____ *3rd*

Patient Age: _____

Gender: _____ *Male* _____ *Female*

Type of impression material used:

Tray adhesive used:

Aquasil Ultra Cordless

Aquasil Ultra

Yes *No*

Tray material:

Metal stock *Plastic stock* *Custom* *Plastic dual arch* *Metal dual arch*

Type of tray used:

Ant quad *Post quad* *Full arch*

Number of units requested:

2-3 FDP *Onlay* *Single crown x _____*

Anterior *Canine* *Premolar* *Molar*

Jaw: *Maxillary* *Mandibular*

Time Required for 1st Impression: _____ minutes and seconds

Number of Impressions Required to Obtain Adequate Impression: _____

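### The adjusted model leaves out tooth position and number of units, both already on the clinician form, so the secondary jaw estimate may be confounded

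*Combined protocol and SAP*

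**What the plan says.** The Statistical Analysis section sets two layers of analysis. For technique, "the Wilcoxon rank sum test will be used as the primary statistical test", and it is unadjusted. A supporting model follows: "To adjust for additional covariates [clinic providing care, jaw, procedural materials], Poisson regression will be used", "including impression group with a primary interest in estimation using confidence intervals". No other covariate is named, and procedural materials are not defined.

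Specific Aims lists, among the secondary aims, the effect of "jaw of restoration placement (maxillary vs mandibular) on the outcomes of accuracy, time, and discomfort".

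The treating-clinician form has a tooth-position item ("Anterior *Canine* *Premolar* *Molar") and an item on units requested ("2-3 FDP *Onlay* *Single crown x", followed by a blank for a count). Methods confirms that the clinician records "the type of tray used; the number of units requested".

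Three design facts in Methods bear on the point. Allocation is stratified by clinic only, in blocks of four. The envelope is opened once the tooth has been prepared. One tooth per patient, the most posterior, is evaluated, and its impression is finished before work on other teeth.

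**The concern.** Technique is randomised, so its comparison does not rely on covariates for validity. Jaw is different: which jaw is treated follows from the patient's needs. If the lower-jaw study teeth are more often molars than the upper-jaw ones, and molars give more errors, longer times or more discomfort, a model without tooth position credits part of the molar effect to jaw.

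Number of units raises a similar issue. Methods tells patients that having several teeth planned may lengthen the appointment, and the discomfort score sums four ratings, the last taken at the end of the appointment. In the cordless arm, cartridge size also depends on how many teeth are prepared. Extent of treatment could therefore plausibly relate to the outcomes.

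The stake is the answer to a stated secondary aim. The adjusted model exists mainly for estimation, so an avoidable distortion in one of its estimates matters even in an exploratory study. Both variables are normally settled before allocation, so they are legitimate baseline covariates.

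**Working it through.** **The plan's own figure.** Noether's formula with P = 0.709, 80% power and two-sided alpha 0.05: total N = (1.960 + 0.842)² / [3 × (0.709 − 0.5)²] = 7.85 / 0.131 = 59.9, or 30 per group, as stated. This rests on the Wilcoxon test alone, so the covariate list does not affect it.

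**Jaw.** Let p1 and p0 be the molar shares among study teeth in the two jaws, and R the ratio of mean outcome, molar to non-molar. With no true jaw effect, a log-linear model without position gives

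spurious jaw ratio = [1 + p1(R − 1)] / [1 + p0(R − 1)].

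The documents give none of p1, p0 or R. All values below are assumptions.

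| Molar shares | R = 1.25 | R = 1.5 | R = 2 |
|---|---|---|---|
| 50% v 50% | 1.00 | 1.00 | 1.00 |
| 55% v 45% | 1.02 | 1.04 | 1.07 |
| 60% v 40% | 1.05 | 1.08 | 1.14 |
| 70% v 40% | 1.07 | 1.13 | 1.21 |

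Larger gaps:
- 80% v 50%, R = 2: 1.8 / 1.5 = 1.20.
- 80% v 60%, R = 1.5: 1.4 / 1.3 = 1.08.
- 80% v 40%, R = 3: 2.6 / 1.8 = 1.44, the extreme case.

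**Technique.** A Poisson simulation (800 runs per setting) assumed a corded mean of about 3 errors, a true technique rate ratio of 0.70 and molar shares of 60% v 40% by jaw. Position and a three-level restoration type were both prognostic with ratio R. The model was fitted with and without those two covariates. Entries are for the log rate ratio for technique, without → with.

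| n | R | Actual SD | Model-based SE | Robust SE |
|---|---|---|---|---|
| 60 | 1.0 | 0.165 → 0.173 | 0.170 → 0.175 | 0.161 → 0.161 |
| 60 | 1.25 | 0.181 → 0.180 | 0.169 → 0.174 | 0.165 → 0.160 |
| 60 | 1.5 | 0.184 → 0.164 | 0.166 → 0.172 | 0.174 → 0.158 |
| 60 | 2.0 | 0.211 → 0.170 | 0.161 → 0.167 | 0.194 → 0.152 |
| 100 | 1.0 | 0.134 → 0.136 | 0.130 → 0.132 | 0.126 → 0.126 |
| 100 | 1.25 | 0.136 → 0.134 | 0.129 → 0.131 | 0.129 → 0.125 |
| 100 | 1.5 | 0.143 → 0.132 | 0.127 → 0.129 | 0.136 → 0.124 |
| 100 | 2.0 | 0.149 → 0.118 | 0.122 → 0.125 | 0.154 → 0.118 |

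The estimated technique ratio stayed at 0.69 to 0.70 throughout, so the omission does not bias it. The actual SD falls by 8% (n = 100) to 11% (n = 60) at R = 1.5 and by 19% to 21% at R = 2. It does not improve materially at R = 1.25 or below. The model-based SE rises slightly in every row.

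The gain also depends on the error rate. For one binary covariate the variance ratio, without to with, is 1 + mean × CV², where CV² = p(1 − p)(R − 1)² / [1 + p(R − 1)]². With 65% molars and R = 2, CV² = 0.2275 / 2.7225 = 0.084. A mean of 0.5 errors gives 1.04; a mean of 1.7 gives 1.14. The documents state only that errors can run from 0 to 13.

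**Degrees of freedom.** If every recorded material is entered, the planned terms besides impression group take clinic 2 + jaw 1 + adhesive 1 + tray material 4 + tray type 2 = 10, or 11 with impression material. Full coding of position (3), restoration type (2) and units (1) would add 6; two binary terms add 2.

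**The case against.** The strongest reply is that confounding has not been shown. It needs position or units both to differ by jaw and to affect the outcome, and the documents report neither. Choosing the most posterior tooth also pulls multi-tooth patients towards posterior teeth in both jaws, which narrows the variation. This stands: a reader might infer that the jaw effect is confounded, but the documents support only that it may be. A range of 1.08 to 1.44 taken alone would also mislead, because each cell assumes a molar-share gap of at least 20 points and R of at least 1.5; equal shares give 1.00.

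A reader might also infer that the technique result is biased, or that its intervals would narrow with the extra terms. Neither follows. Technique is randomised within clinic, its primary test is unadjusted, and the plan names no robust or overdispersion-adjusted standard error through which a precision gain would appear.

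A third reply is that procedural materials may include tray type (anterior quadrant, posterior quadrant, full arch), which partly stands in for position. That helps little: a full-arch tray says nothing about position, a posterior-quadrant tray does not separate premolars from molars, and tray choice may follow allocation.

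Finally, adding position, restoration type and units in full is costly for 60 to 100 patients, and type and units share one form item. This stands and calls for a shorter list. It is also fair that adjusting for impression material, which largely coincides with the arm, is a separate and possibly larger problem in the same sentence. It does not remove this one.

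**Conclusion.** The point holds in limited form. The adjusted model omits two recorded variables that are normally fixed before allocation, and one of its targets, jaw, is a non-randomised secondary aim. The possible distortion of the jaw ratio runs from none, through about 1.2 under moderate assumed imbalance, to 1.44 in an extreme case. Those figures rest wholly on assumed molar shares and molar ratios. The formula applies to any outcome modelled on the log scale, but R may differ between errors, time and discomfort.

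The technique effect, its primary test and the sample size are untouched. Greater true precision for technique is possible only if the covariates are strongly prognostic, and is not a main reason for the change. Severity is minor to moderate, limited mainly to the jaw aim.

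**What to change.** In the Statistical Analysis section, add two prespecified binary terms to the covariate list for all three primary outcomes, chiefly for the jaw estimate: molar versus non-molar for the study tooth, and single versus multiple units. Leave restoration type out, because it overlaps with units on the form.

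State the coding before any outcome data are seen. Tooth position should refer to the evaluated tooth, as it stood when the envelope was opened. The units item shows a count only beside single crowns, so a rule is needed for classing onlays as single or multiple.

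The cost is 2 degrees of freedom, one or two sentences of text and no new data collection. Jaw results should still be reported as non-randomised associations.
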